#### **11.4.4 Safety Laboratory Parameters**

Descriptive statistics will be presented for baseline values, absolute values, and changes from baseline in safety laboratory parameters. Laboratory data will be summarized in tables and presented in figures by the type of laboratory test.

#### **11.4.5 Vital Signs**

Vital signs will be listed.

#### **11.4.6 Electrocardiogram**

Abnormal ECG-observations will be listed and summarized. The ECG data will be summarized for the SAF.

#### **11.4.7 Analyses of Anti-tumor Activity**

The efficacy analyses will be based on the FAS.

##### **11.4.7.1 Imaging Data**

All imaging data will be listed. Reduction in tumor sizes will be analyzed by summarizing the measures of the target lesions, including the relative change (%) from baseline. Graphs of the individual patient profiles over time of the (i) sum of measures and (ii) relative change in the sum of measures from baseline will be presented.

The best relative change from baseline will be presented in a waterfall plot.

##### **11.4.7.2 Response Evaluation**

The responses will be evaluated according to both RECIST 1.1 and iRECIST.

#### **RECIST 1.1**

The OR is the best timepoint response recorded from the start of the study treatment until the EOT. Patients who obtain CR and PR are considered responders. Both confirmed and unconfirmed responses will be presented. Patients are considered non-responders if they obtain SD, PD, or “Not evaluable” as OR.

SD requires that post-baseline measurements have met the SD criteria at least once and for a minimum period of 4 weeks ( $\pm$  7 days).

The OR rate will be presented including corresponding, for binomial distribution, exact 95% confidence intervals.

The DCR as well as proportions of patients in disease control at 4, 8, 16, and 24 weeks ( $\pm$  7 days for each of the timepoints) will be analyzed and presented in the same way as OR.

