m: CT scan of the neck, chest, and abdomen at screening and Week 4, 8, 16, and 24, with an assessment window of  $\pm 4$  days. Confirmatory scanning for patients who have obtained PR or CR will be undertaken approximately 4 weeks after the initial response.

n: Only if more than 6 weeks since last CT scan

o: Assessment of response by the Primary Investigator (progression and survival).

p: Pre-dose on Day 1 and 8 of Cycle 1, Day 1 of Cycles 2-13, and EOT.

q: Vital signs to be monitored and registered every 2 hours on Day 1 and Day 2 of cycle 1 and cycle 2 during daytime and every 4 h during nighttime.

r: Cycle 1 day 1 the IL-6 sample must be taken pre-dose (baseline), all other IL-6 samples should be taken the day after IMP administration (dosing day +1) and should be taken at the same time of the day ( $\pm 60$  min)

s: ECG performed pre-dose on dosing days.

Table 3-2 Schedule of time and events: phase 2 (dose expansion)

Treatment / Measurements / Evaluations	SCR	Cycle 1 (D1 to 14); 1 cycle = 14 days a DLT evaluation period = 2 cycles								Cycle 2 to 13				EOT ±4d	Follow up d
		<21 days	■	■	■	■	■	■	■	■	■	■	■		
Informed consent	X														
Eligibility check	X														
Demographics and baseline characteristics	X														
Medical history, concomitant illness	X														
Concomitant medication	X	X	X	X	X	X	X	X	X	X	X	X	X	X e	
Physical examination	X f	X	X			X	X			X				X f	
Height	X														
Weight	X	X				X			X	X				X	
ECOG score	X	X								X				X	X
Vitals signs	X	X g	X g	X	X	X g	X g	X	X	X g	X g	X	X	X	
HCG in FOCP (urine or blood)	X										X g				X
Urinalysis (dipstick)	X	X				X				X					X
Cranial and Spinal MRI h	X														
ECG	X	X s	X			X s	X			X s	X				
Echocardiogram/MUGA	X								X i					X i	
Hospitalization j		X	X			X	X			X	X				
Premedication		X	X			X	X			X	X				
███████████		■													
███████████						X				X					
PK, see Table 8-1		X	X							X					
AE (CTCAE version 5)	X k	X	X	X	X	X	X	X	X	X	X	X	X	X	X
CRS grading l		X	X	X	X	X	X	X	X	X	X	X	X	X	
ICE score l		X	X	X	X	X	X	X	X	X	X	X	X	X	
Hematology	X	X	X	X	X	X	X	X	X	X	X	X	X	X	
Clinical chemistries	X	X	X	X	X	X	X	X	X	X	X	X	X	X	
Coagulation	X	X	X	X	X	X	X	X	X	X	X	X	X	X	

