### 6.2.11 End of Treatment Visit

At both phase 1 and phase 2, an “end of treatment” (EOT) visit should be made when the patient completes treatment or permanently discontinues the IMP. The EOT visit will be performed at the time of discontinuation, within 30 days after the last IMP dose and prior to initiation of any new anticancer treatment. In case of premature study discontinuation, the EOT visit should be performed immediately. The reason for discontinuation from treatment must be documented in the eCRF.

The EOT visit will include the following assessments: physical examination, vital signs and body weight, ECOG performance score, neurological examination, recording of concomitant medication and concurrent procedures, safety laboratory assessments (hematology, coagulation and clinical chemistry), HCG test (for females of childbearing potential), anti-drug antibodies, AEs/SAEs, urinalysis, and CT scanning of the primary tumor site (if the last prior tumor assessment was >6 weeks from date of the EOT visit).

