### 6.3.3 Premature Discontinuation of Treatment

#### 6.3.3.1 Treatment Discontinuation Criteria

A patient should be discontinued from treatment with the IMP if any of the following situations occur:

- Any DLT (see section 6.2.3)
- Disease progression - confirmed PD (confirmed immune PD [iCPD]) or as clinically judged by the Investigator
- Patients with suspected progression, i.e., unconfirmed PD (unconfirmed immune PD [iUPD]), are allowed to continue treatment if they are considered to be clinically stable in the opinion of the Investigator until confirmatory radiological assessment (CT scan) is performed.
- In case of decreased ejection fraction (EF) of grade 3 (EF, 39%–20% or  $\geq 20\%$  drop from baseline), and the event is considered treatment-related.
- Investigator's decision for medical or safety reasons
- If the patient receives prohibited anti-tumor therapy/procedures during the trial
- Patient chooses to withdraw from the therapy at any time
- Pregnancy

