#### **11.4.7.4 Duration of Response**

The DoR and iDoR are calculated, censored, and presented in the same way as PFS and iPFS, respectively, above with the following differences:

- DoR and iDoR are derived for responders only
- DoR and iDoR begin at the timepoint when the criteria for response are first met.

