#### **11.4.14 Handling of Missing Data**

Missing safety data will in general not be imputed. In the analyses of OR, patients with evaluable disease at baseline but who cannot be evaluated for response will be considered as non-responders.

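### RECIST 1.1 overall response is counted to end of treatment with no cut-off at RECIST progression, so a response after progression counts and conflicts with PFS and DoR

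*Combined protocol and SAP*

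**What the plan says.** Section 11.4.7.2, under RECIST 1.1, sets the response window in one sentence: "The OR is the best timepoint response recorded from the start of the study treatment until the EOT". Patients with CR or PR are responders. On confirmation, "Both confirmed and unconfirmed responses will be presented". On precision, "The OR rate will be presented including corresponding, for binomial distribution, exact 95% confidence intervals". DCR and the proportions in disease control at 4, 8, 16 and 24 weeks are handled in the same way. Neither this section nor any other closes the window at the first RECIST 1.1 progression.

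Treatment need not end at that progression. Section 6.3.3.1 says that patients with suspected, unconfirmed progression "are allowed to continue treatment if they are considered to be clinically stable in the opinion of the Investigator", until a confirmatory CT is done. Section 8.2 gives the reason: iRECIST is applied so that pseudo-progression does not take patients off treatment.

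Section 11.4.7.3 runs PFS from first dose to progression or death, whichever is first. Its rule for setting aside an unconfirmed progression that is followed by stability or response is written for iPFS only. Section 11.4.7.4 carries the PFS rules over to duration of response, with one change of origin: "DoR and iDoR begin at the timepoint when the criteria for response are first met". Section 11.4.7.2 also has a separate iRECIST part with its own definition of a responder.

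**The concern.** Best response up to EOT equals best response up to progression only if treatment stops at progression. This trial deliberately lets some patients continue past a first RECIST progression. For them the RECIST 1.1 response window stays open after the RECIST 1.1 PFS clock has stopped.

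Two things are at stake. The first is coherence. One patient could be a RECIST responder whose response starts after the RECIST progression, and DoR then has no sensible value under the plan's own rules. The second is interpretation. The plan reports RECIST 1.1 and iRECIST separately, and a reader will take the RECIST figure as activity before progression. If responses after progression enter it, the two response rates no longer differ in the way the plan intends.

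**Working it through.** **The plan's own figure.** The plan states no ORR hypothesis, power or target. The only figure covering the phase 2 sample size is Table 11-1, the chance of seeing at least one event, 1 − (1 − p)^N. For N = 30 and p = 5% this is 1 − 0.95^30 = 78.5%, printed as 79%, and all 24 cells reproduce. It confirms N = 30 but says nothing about response, so the check rests on setting the sections side by side.

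**Inputs.** CT at weeks 4, 8, 16 and 24, ±4 days (Tables 3-1 and 3-2, footnote m). Up to 13 cycles of 14 days, that is 13 × 14 = 182 days or 26 weeks (section 6.2.1.1). Confirmatory scan about 4 weeks after a first response (section 8.2). Phase 2 N = 30 (section 6.3.1).

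**One patient through the rules.** Suppose the week 4 CT is RECIST PD, the patient is clinically stable and continues, and the week 8 CT is PR. The progression was not confirmed, so unless the investigator judges otherwise the confirmed-progression criterion in section 6.3.3.1 is not met and treatment goes on. EOT therefore falls after week 8.

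| Endpoint | Rule | Result |
|---|---|---|
| RECIST 1.1 OR | best timepoint response to EOT (11.4.7.2) | PR, responder |
| RECIST 1.1 PFS | first dose to first progression or death (11.4.7.3) | event at week 4 |
| RECIST 1.1 DoR | starts when response is first met, otherwise as PFS (11.4.7.4) | starts week 8, ends week 4: 4 − 8 = −4 weeks |
| iRECIST response | iPR makes a responder (11.4.7.2) | responder |
| iPFS | unconfirmed progression set aside after later iPR (11.4.7.3) | no event at week 4 |

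The iRECIST rows agree with each other. The RECIST 1.1 rows do not.

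Reporting confirmed responses as well does not remove the problem. A PR at week 8 with a confirming scan at about week 12 is a confirmed response that still follows the week 4 progression.

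**Size.** One patient moves a 30-patient ORR by 1/30 = 3.3 points. The documents give no frequency, so the counts below are assumed. The intervals are exact (Clopper-Pearson) 95%.

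| Responses after PD removed from an assumed 5 | ORR | 95% CI |
|---|---|---|
| 0 | 5/30 = 16.7% | 5.6 to 34.7 |
| 1 | 4/30 = 13.3% | 3.8 to 30.7 |
| 2 | 3/30 = 10.0% | 2.1 to 26.5 |

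The plan fixes no stratum sizes. With two equal platinum strata of 15 (an assumption), one patient is 1/15 = 6.7 points. In the DoR analysis, one of 5 responders is 20% of the set.

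**The case against.** The strongest reply is that section 8.2 bases response on the RECIST 1.1 criteria, which may themselves settle what happens after progression. Their text is not in the documents, so I do not judge that. The reply still does not close the gap, because section 8.2 sends the reader to section 11 for the definitions of response, and section 11 states an explicit window. A programmer following it would use EOT. Section 11.1 leaves further detail to the SAP, but that does not alter a window already written.

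It is also fair that only clinically stable patients awaiting a confirmatory scan are affected, that no success rule uses ORR, and that the intervals above overlap heavily. These points limit the size and stand.

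A reader might go further and infer three things that the documents do not support.

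- *That the EOT cut-off loses responses in patients stopped early for a DLT.* The EOT CT is required "Only if more than 6 weeks since last CT scan". With a screening CT s days before Day 1, that means EOT after Day 43 − s: Day 22 for s = 21, Day 42 for s = 1. A patient with EOT by Day 22 thus has no required post-baseline CT, since the week 4 window is Days 24 to 32. But any response recorded by EOT is kept, and the patient stays in the denominator. Section 11.4.14 says that "patients with evaluable disease at baseline but who cannot be evaluated for response will be considered as non-responders", a stated and conservative choice that applies to early stopping for any reason. Although "The EOT visit will be performed at the time of discontinuation", section 6.2.11 also allows up to 30 days after the last dose, so the week 4 CT can precede it. Follow-up CTs are reports at 8-weekly or local timing (section 6.2.13), so counting them would be a trade-off rather than a correction.
- *That responses to a new therapy are counted.* Section 6.2.11 places EOT before any new anticancer treatment, and prohibited anti-tumor therapy ends trial treatment (section 6.3.3.1). The EOT cut-off already excludes nearly all of these.
- *That ORR will be pushed past the 15% in section 4.1.* That figure is background text, not a threshold, and no rate of response after progression is given.

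**Conclusion.** The point holds for responses after progression. As written, RECIST 1.1 OR can include a CR or PR recorded after RECIST 1.1 progression, and such a patient has contradictory RECIST results for OR, PFS and DoR. The contradiction lies within sections 6.3.3.1, 8.2 and 11.4.7 and needs no outside source.

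The effect is 3.3 points of ORR per patient at N = 30, upward only, in an unknown and probably small number of patients. That it is small is my judgement, based on the restriction to clinically stable patients awaiting a confirmatory scan. Error rates, power and escalation rules are unaffected. The change is worth making because the definition cannot be programmed consistently with DoR as it stands.

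**What to change.** In section 11.4.7.2, and in the SAP text that follows from it:

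- Define RECIST 1.1 OR and DCR as the best timepoint response from first dose until the first RECIST 1.1 progression or EOT, whichever is earlier.
- State that responses recorded after RECIST 1.1 progression count only toward the iRECIST endpoints.
- Apply the same cut-off to the RECIST 1.1 proportions in disease control at 4, 8, 16 and 24 weeks, since they are analysed in the same way as OR.
- In section 11.4.7.4, restrict RECIST 1.1 DoR to responses that begin within this window, so that the start cannot follow the progression date.

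The cost is wording only, with no added scans, visits or patients. RECIST 1.1 ORR may be slightly lower, and responses after an unconfirmed progression remain visible in the iRECIST results.

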## **iRECIST**

Responses assigned using iRECIST have a prefix of “i” (immune): iCR, iPR, iSD, iUPD, or iCPD to differentiate them from responses assigned using RECIST 1.1. Patients who obtain iCR and iPR are considered responders. Patients are considered non-responders if they obtain iSD, iUPD, iCPD or Not Evaluable as iOR. For iDCR, patients are considered to be in disease control if the corresponding response is iCR, iPR, or iSD. iSD requires that post-baseline measurements have met the iSD criteria at least once and for the same time-period as SD.

The iRECIST response endpoints are analyzed using the same statistical methodology and the results presented in the same way as for the corresponding RECIST 1.1 endpoints.

### **11.4.7.3 Progression-free Survival**

PFS and iPFS are derived as the time from the first dose administration until progression or death, whichever occurs first.

The progression date to be used for calculation of iPFS should be the first date at which progression criteria are met (i.e, the date of iUPD) provided that iCPD is confirmed at the next assessment. If iUPD occurs, but is disregarded because of later iSD, iPR, or iCR, that iUPD date should not be used as the progression event date.

If progression is not confirmed and there is no subsequent iSD, iPR, or iCR, the iUPD date should still be used if:

- the patient stops protocol treatment because they were not judged to be clinically stable, or
- no further response assessments are done (because of patient refusal, protocol non-compliance, or patient death), or
- the next timepoint responses are all iUPD, and iCPD never occurs, or
- the patient dies from their cancer.

PFS and iPFS will be derived for all patients and presented graphically as well as summarized using survival analysis methods: distribution functions will be estimated using the Kaplan-Meier technique and plotted. The corresponding Kaplan-Meier quartile estimates including 2-sided 95% confidence intervals will be presented.

PFS and iPFS will be censored on the date of the last adequately evaluable tumor assessment for patients who do not have an event (progression or death), for patients who start new anti-cancer

treatment prior to an event, or for patients with an event after 2 or more consecutive missing tumor assessments.

Patients who do not have a baseline tumor assessment or who do not have any post-baseline tumor assessments will be censored on the date of the first treatment unless death occurred on or before the time of the second planned tumor assessment, in which case the death will be considered an event.

#### **11.4.7.4 Duration of Response**

The DoR and iDoR are calculated, censored, and presented in the same way as PFS and iPFS, respectively, above with the following differences:

- DoR and iDoR are derived for responders only
- DoR and iDoR begin at the timepoint when the criteria for response are first met.

#### **11.4.8 Overall Survival**

OS is defined as the time from the first dose administration until death. OS will be analyzed using the same Kaplan-Meier methodology as for PFS above, except that in the absence of an observed event, OS is censored on the latest day that the patient is known to be alive as per assessment or contact.

#### **11.4.9 PK Analysis**

The PK information will be summarized for the PKAS.

All PK-concentrations and PK-parameters will be presented in listings.

Individual curves of nivatrotamab concentrations, including information on actual dose, will be presented for all patients. All available data will be shown in these figures. Both actual as well as ln (log)-transformed values will be presented. In the graphical presentations, values below the lower level of quantification (LLOQ) will be set to LLOQ/2 and marked with a “<LLOQ.” Any values above the upper level of quantification (ULOQ) will be marked with a “>ULOQ.”

PK parameters ([Table 11-2](#)) will be calculated based on non-compartmental methods.

**Table 11-2 List of PK parameters**

Parameter	Description
$C_{\max}$	The maximum (peak) observed drug concentration after a single dose administration
$T_{\max}$	The time to reach maximum (peak) drug concentration in serum after a single dose administration.
$AUC_{0-T}$	The area under the serum concentration–time curve from time zero to the last quantifiable timepoint (T).
$AUC_{0-\infty}$	The area under the serum concentration–time curve from time zero to infinity
$T_{1/2}$	The elimination half-life associated with the terminal slope ( $\lambda_z$ ) of a semi-logarithmic concentration–time curve.
CL	The total body clearance of drug from serum.
$V_d$	Volume of distribution

The relation between derived PK parameters and covariates such as actual dose, weight, and selected parameters will be evaluated graphically.

If deemed applicable, compartmental modeling approaches to parameter estimation will be applied.

The PK-parameters will be presented in summary tables where AUC and  $C_{\max}$  will be summarized using the geometric mean and the coefficient of variation (CV) that is based on a log-normal distribution:  $CV(\%)=100 \cdot \sqrt{e^{\sigma_{ln}^2} - 1}$ .

The half-life will be summarized using the harmonic mean.

In support of the RP2D-selection, analyses of a relation between exposure and response will be performed:

- Exposure after Cycle 1
  - $C_{\max}$
  - $AUC_{0-\infty}$
- Response
  - Efficacy at weeks 4 and 8
    - Disease control [RECIST & iRECIST] (yes/no)
    - Reduction in tumor size (Section 11.4.7.1)
  - Safety after Cycle 1, 2 and 4
    - CRS (yes/no)
    - Highest grade of CRS
    - SAE (yes/no)

by means of logistic regressions (with ordinal response variable for highest grade of CRS, as appropriate) or linear regression for Reduction in tumor size. Non-linear PK/PD-modelling of the above will be considered.

Further details of the analyses and results presentations will be presented in a separate plan.

#### **11.4.10 Analysis of Anti-Drug Antibody Formation**

Immunogenicity data will be listed and positive/negative host immune response to nivatrotamab and presence of binding antibodies will be summarized (positive/negative).

The immunogenicity information will be summarized for the SAF.

#### **11.4.11 Exploratory Objectives**

GD2 expression from tumor tissue will be summarized and presented graphically.

The results from these exploratory analyses may be presented in a separate report.

#### **11.4.12 Interim Analysis**

No formal interim analyses are planned. Ad-hoc interim analyses may be performed in relation to health authority interactions.

#### **11.4.13 Subgroup Analyses**

No subgroups beyond the sensitivity/resistance to previous platinum therapy strata in phase 2 are defined.

#### **11.4.14 Handling of Missing Data**

Missing safety data will in general not be imputed. In the analyses of OR, patients with evaluable disease at baseline but who cannot be evaluated for response will be considered as non-responders.

### **11.5 Reporting of Trial Results**

The results from this trial will be presented in a clinical trial report (CTR) after the last patient in the dose expansion has reached the end of the trial.

## 12 ETHICS

### 12.1 Independent Ethics Committee (IEC) or Institutional Review Board (IRB)

This protocol and any accompanying material to be provided to the patient (such as patient information sheets and/or descriptions of the trial used to obtain informed consent) will be submitted by the Investigator to an IRB/IEC. Approval from the IRB/IEC must be obtained before starting the trial and should be documented in a letter to the Investigator.

It is the responsibility of the Investigator or his/her representative to obtain approval from the IRB/IEC before enrollment of any patient into the trial for the trial protocol/protocol amendments, advertisements, the patient information and the Informed Consent, including any written material to be given to the patient.

### 12.2 Ethical Conduct of the Trial

The trial will be conducted in accordance with the protocol, applicable regulatory requirements, International Council on Harmonisation (ICH) Good Clinical Practice () (GCP) and the ethical principles of the Declaration of Helsinki () as adopted by the 18th World Medical Assembly in Helsinki, Finland, in 1964 and sub-sequent versions.

The trial will be conducted according to FDA regulations relating to GCP and clinical trials, Protection of Human Subjects (21 CFR Part 50) and as per Ethical Considerations for Clinical Trials on Medicinal Products Conducted with the Pediatric Population (recommendations of the ad hoc group for the development of implementing guidelines for Directive 2001/20/EC relating to GCP in the conduct of clinical trials on medicinal products for human use). The guideline is referenced on internet address [http://ec.europa.eu/health/files/eudralex/vol-10/ethical\\_considerations\\_en.pdf](http://ec.europa.eu/health/files/eudralex/vol-10/ethical_considerations_en.pdf).

